4.1.3 Follow-up Period

All subjects will have a follow-up contact (site visit or telephone call, at the discretion of the Investigator) 30 days after the last patch is removed. This contact will be used to collect information about any AEs or SAEs that may have occurred since discharge and to follow-up on any AE that was on-going at discharge.

The Schedule of Events is presented in [Table 1](#).

Noven Pharmaceuticals, Inc.
HP-3070-GL-04
HP-3070

Table 1 Schedule of Events

Study Period	Screening/ Single-blind Placebo Run- In Period [a]	Double-Blind Treatment Period							Safety Follow-up Visit or Telephone Call [b]
		Week/Day	3 to 14 days	Baseline Day 0 [c]	Day 7/ Wk 1	Day 14/ Wk 2	Day 21/ Wk 3	Day 28/ Wk 4	
Visits	1	2	3	4	5	6	7	8	8
Informed consent	X								
Pre-randomization form	X								
Assign subject number from IWRS	X								
Inclusion/exclusion criteria	X	X							
Demographics	X								
Physical examination including skin examination	X							X	
Medical history including psychiatric history	X								
MINI [d]	X								
PANSS [d]	X	X	X	X	X	X	X	X	
CDSS [d]	X	X	X	X	X	X	X	X	
C-SSRS [d]	X	X	X	X	X	X	X	X	
CGI-S [d]	X	X	X	X	X	X	X	X	
CGI-I [d]			X	X	X	X	X	X	
AIMS [d]	X	X	X	X	X	X	X	X	
SAS and BARS [d]	X	X	X	X	X	X	X	X	
MSQ [d]	X			X		X		X	
Vital signs [e]	X	X	X	X	X	X	X	X	
Weight and height [f]	X	X	X	X	X	X	X	X	
Standard 12-lead ECG [g]	X	X	X	X	X	X	X	X	
Clinical laboratory testing (fasting)	X	X			X			X	
Urine drug screen/blood alcohol [h]	X								
Serum/urine pregnancy test [i]	X	X	X	X	X	X	X	X	
Serology (HIV, HBsAg, anti-HCV) [j]	X								
Concomitant therapies	X	X	X	X	X	X	X	X	X

Noven Pharmaceuticals, Inc.
HP-3070-GL-04
HP-3070

32

Study Period	Screening/ Single-blind Placebo Run- In Period [a]	Double-Blind Treatment Period							Safety Follow-up Visit or Telephone Call [b]
		Week/Day	3 to 14 days	Baseline Day 0 [c]	Day 7/ Wk 1	Day 14/ Wk 2	Day 21/ Wk 3	Day 28/ Wk 4	
Visits	1	2	3	4	5	6	7	8	8
Adverse events	X	X	X	X	X	X	X	X	X
PK blood samples [k]					X			X	
Blood sample for prolactin level [l]		X			X			X	
Dispense run-in kit	X								
Randomization/ assign double-blind kit		X							
Provide subject identification card	X								
Dosing with single-blind patch (patch application and removal of previous patch, if applicable)	X								
Dosing with double-blind patch (patch application and removal of previous patch, if applicable)		X	X	X	X	X	X	X	
Skin Irritation Assessment [m]	X	X	X	X	X	X	X	X	
Patch Adhesion Assessment [m]	X	X	X	X	X	X	X	X	
Patch Discomfort Assessment [m]	X	X	X	X	X	X	X	X	
Adhesive Residue Assessment [m]	X	X	X	X	X	X	X	X	
Drug accountability	X	X	X	X	X	X	X	X	

AIMS = Abnormal Involuntary Movement Scale; BARS = Barnes Akathisia Rating Scale; CDSS = Calgary Depression Scale for Schizophrenia; CGI-I = Clinical Global Impression - Improvement scale; CGI-S = Clinical Global Impression - Severity of Illness scale; C-SSRS = Columbia-Suicide Severity Rating Scale; ECG = electrocardiogram; ET = end of treatment; HBsAg = hepatitis B antigen; HCV = hepatitis C virus; HIV = human immunodeficiency virus; IWRS = Interactive Web-Based Response System; MINI = Mini International Neuropsychiatric Interview; MSQ = Medication Satisfaction Questionnaire; PANSS = Positive and Negative Syndrome Scale; PK = pharmacokinetics; SAS = Simpson Angus Scale; Wk = week

- The subject must use the single-blind placebo patch for a minimum of 3 days prior to entering the double-blind Treatment Period. Washout of the subject's current antipsychotic and other prohibited medications must be completed by the end of the Screening/Run-in Period. Subjects who have a decrease in PANSS total score $\geq 20\%$ from Screening to Baseline or a PANSS total score < 80 at Screening or Baseline will be discontinued from the study.
- Subjects will have a follow-up contact (site visit or telephone call, at the discretion of the Investigator) 30 days after the last patch is removed.
- All baseline assessments and laboratory samples will be performed prior to randomization.
- It is suggested that assessment scales should be performed in the order they appear in the Schedule of Events

Noven Pharmaceuticals, Inc.
HP-3070-GL-04
HP-3070

33

- e. Blood pressures (sitting) and pulse rates should be measured after subject has rested (sitting quietly) for 5 minutes. In addition, assessments for orthostatic hypotension will be performed at each visit. Blood pressure readings and pulse rate will be obtained after the subject has been supine for 5 minutes. These will be repeated after the subject has been standing up for approximately 1 to 3 minutes.
- f. Height will be obtained at Screening, only.
- g. ECG recordings will be obtained after the subject has been supine and at rest for at least 5 minutes.
- h. Urine drug screen and alcohol breathalyzer test should be completed if the subject leaves the study site.
- i. All positive urine pregnancy test results must be confirmed by a serum test. Subjects with positive urine and serum pregnancy test results at screening must not be enrolled. Subjects with positive urine and serum pregnancy test results during the trial must discontinue treatment. Urine pregnancy test to be repeated if subject leaves the study site.
- j. Subjects with chronic Hepatitis B or C may be included provided that their condition is stable and that values for liver function tests and other laboratory tests results meet the criteria specified for entry into the study.
- k. At least 3 blood samples will be collected at 2, 14, and 22 hours after application of the patch with \pm 2 hour- window on Day 21 and 42. Actual blood sampling time will be recorded.
- l. The central laboratory will not report prolactin levels to the sites nor the Sponsor, because this could potentially result in unblinding the treatment. The central laboratory will report prolactin levels as “masked” on the laboratory report (see [Section 6.2.2.2.3](#) for more details).
- m. Patch adhesion will be evaluated throughout the day including at the time points during which the site staff collects routine vital signs as per hospital policy/SOP; and immediately prior to removal of previous day’s patch. In addition, subjects will be asked to check patch adhesion throughout the day and report immediately to site personnel if the patch detaches completely or detaches partially (i.e., some edges of the patch are lifting off the skin). Irritation at the site of patch application will be assessed each day between 30 and 60 minutes after patch removal. Subjects will be asked to report to the site staff any discomfort or skin irritation due to the patch. Discomfort and skin irritation reported by the subjects will be recorded as AEs. Patch application site will be assessed weekly for adhesive residue.

Noven Pharmaceuticals, Inc.
HP-3070-GL-04
HP-3070

34

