Single application of a 13.5-mg patch and multiple applications of a 9.0-mg patch resulted in a total of 115 AEs. As a result, the 18.0-mg dose was not administered due to the unfavorable tolerability profile of 13.5 mg in healthy volunteers. Further, only 3 subjects among the 11 subjects who started multiple applications of the 9-mg patch completed the 7-day multiple applications. No deaths or other serious adverse events (SAEs) occurred during this study. As healthy volunteers were not able to tolerate higher doses and multiple doses of HP-3070, this study in healthy volunteers (HP-3070-US-02) was stopped early and a multiple dose PK study (HP-3070-US-02b) was conducted in patients diagnosed with schizophrenia.

The statistical analysis of relative exposure for both asenapine and desmethyl-asenapine were within the 80% to 125% limits for both dose-normalized C_{max} and AUC, confirming the dose-proportionality between the 9.0-mg and the 13.5-mg HP-3070 patches. These similar desmethyl-asenapine/asenapine ratios and the percentage of the drug released between 9.0 mg and 13.5 mg HP-3070 patches corresponded well to the dose-proportionality results for C_{max} and AUC.

HP-3070-US-02b was an open-label, non-randomized, multiple-ascending dose study designed to evaluate the PK of asenapine and dopamine D2 receptor occupancy relative to steady state plasma levels in subjects with schizophrenia treated with HP-3070 patches (4.5 mg, 9.0 mg, 13.5 mg, and 18.0 mg) for 7 days.

Plasma asenapine concentrations following multiple ascending doses 4.5 mg, 9.0 mg, 13.5 mg, and 18.0 mg of HP-3070 patches increased with increasing dose. The estimated slopes for the steady state C_{max} , C_{min} , and AUC_{0-24} following multiple ascending doses of HP-3070 patches fell within the pre-defined criteria, confirming the dose-proportionality between 4.5 mg and 18.0 mg of HP-3070 patches. These similar desmethyl-asenapine/asenapine ratios and percentage of drug released among all 4 dosages corresponded well to the dose-proportionality results. Plasma asenapine concentration reached the steady state at around 72 hours after the first patch and showed sustained plasma concentrations at steady state.

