4.1.2 Double-blind Treatment Period

Eligible subjects will be randomized at Baseline (Day 0) and randomly assigned to HP-3070 (9.0 mg or 18.0 mg) or placebo in a 1:1:1 ratio. Subjects will receive treatment with study medication daily starting on Day 1 and up to Day 42 for a total of 6 weeks.

Efficacy and safety data will be collected in accordance with the Schedule of Events.

Blood samples will be collected at pre-determined time points and analyzed for asenapine and desmethyl asenapine concentrations.

At discharge (Week 6 or early termination [ET]), the subject will be prescribed an approved antipsychotic treatment and returned to the care of their physician.

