 - i. QT interval corrected using Fridericia's formula (QTcF) ≥ 450 msec (males), QTcF ≥ 470 msec (females)
 - j. Prolactin. The enrollment of subjects with prolactin levels equal or higher than 5 X ULN should be discussed with the Medical Advisor
 16. Subject with hypothyroidism or hyperthyroidism (unless condition has been stabilized with medications for at least the past 90 days); subjects with abnormal free T4 and thyroid stimulating hormone (TSH) levels.

Noven Pharmaceuticals, Inc.
HP-3070-GL-04
HP-3070

39

17. Subject is currently treated with insulin for diabetes. Subjects being treated for diabetes with medications other than insulin are eligible for the study if their condition is stable as determined by satisfying ALL of the following criteria:
 - a. HbA1c <7.0%, AND
 - b. Screening glucose \leq 125 mg/dL or \leq 6.94 mmol/L (fasting) or <200 mg/dL or <11.1 mmol/L (nonfasting). Note: If the nonfasting screening glucose is \geq 200 mg/dL or \geq 11.1 mmol/L, subjects must be retested in a fasted state and the retest value must be \leq 125 mg/dL or \leq 6.94 mmol/L, AND
 - c. Subject has been maintained on a stable regimen of oral anti-diabetic medication(s) for at least 28 days prior to Screening or diabetes has been well-controlled by diet for at least 28 days prior to Screening, AND
 - d. Subject has not had any hospitalizations within the 12 months prior to Screening due to diabetes or complications related to diabetes, AND
 - e. Subject's diabetes is not newly diagnosed during Screening
18. Subject has epilepsy or history of seizures, with the exception of a single seizure episode (e.g., childhood febrile, post traumatic).
19. Subject has uncontrolled hypertension (diastolic blood pressure [DBP] >95 mmHg in any position) or symptomatic hypotension, or orthostatic hypotension which is defined as a decrease of \geq 30 mmHg in systolic blood pressure (SBP) and/or a decrease of \geq 20 mmHg in DBP after at least 3 minutes standing compared with the previous supine blood pressure, OR development of symptoms. Note: Blood pressure measurements may be repeated once to ensure reproducibility of the exclusionary result(s) before excluding a subject based on the criteria noted above.
20. Subject has a history of neuroleptic malignant syndrome.
21. Subject has a score of >2 (mild) on any item of the AIMS at Screening.
22. Subject has a score of 5 (severe akathisia) on BARS global clinical assessment of akathisia at Screening.

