5.8 Treatment Interruptions or Modifications

Dose modifications are not permitted. If the patient misses a dose or receives an extra dose for any reason, this should be recorded and discussed with the Medical Advisor.

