6.2.3 Vital Signs, Physical Findings and Other Safety Assessments

Height will be recorded at Screening, only. Weight will be recorded at each visit. A complete physical examination including examination of the head, neck, ears and throat, thorax, abdomen, urogenital, extremities, neurological, and skin and mucosae will be performed at Screening and at end of study. Abnormal physical examination findings at the Screening will be recorded as medical history and abnormal physical examinations findings at subsequent visits will be recorded as AEs.

Vital sign measurements will include temperature, systolic blood pressure (SBP), diastolic blood pressure (DBP), and heart rate. Blood pressures (sitting) and pulse rates should be measured after subject has rested (sitting quietly) for 5 minutes.

In addition, assessments for orthostatic hypotension will be performed. Blood pressure readings and pulse rate will be obtained after the subject has been supine for 5 minutes. These will be repeated after the subject has been standing up for approximately 1 to 3 minutes.

Subjects with a decrease of ≥ 30 mmHg in SBP and/or a decrease of ≥ 20 mmHg in DBP after ≥ 3 minutes standing compared with the previous supine blood pressure, OR development of symptoms are considered to have orthostatic hypotension.

Twelve-lead ECGs will be recorded at Screening and at the visits specified in [Table 1](#). An ECG recordings will be obtained after the subject has been supine and at rest for at least 5 minutes. Additional 12-lead ECGs may be obtained at the Investigator's discretion and should always be obtained if the subject discontinues the study. A central ECG service will be utilized for reading all ECGs in order to standardize interpretations for the safety analysis. In addition, ECG results will be evaluated at the investigational site to monitor safety during the trial. The Investigator or designee will review, sign, and date each ECG reading, noting whether or not any abnormal results are of clinical significance. The ECG will be repeated if any results are considered by the Investigator to be clinically significant.

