8.6.3 Vital Signs Measurements, Physical Findings and Other Safety Evaluations

Descriptive statistics for the change from Baseline will be summarized at each visit for C-SSRS, SAS, BARS, and AIMS.

Mean changes from Baseline and incidence of treatment-emergent abnormal vital signs, weight, and ECG results will be summarized. The number and proportion of subjects with orthostatic hypotension will also be summarized.

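### The standing blood pressure is read at about 1 to 3 minutes, but orthostatic hypotension is defined at 3 minutes or more, so a compliant reading may be unable to meet the definition

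*Protocol*

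**What the plan says.** Table 1, footnote e states that "assessments for orthostatic hypotension will be performed at each visit". Footnote e and Section 6.2.3 give the same procedure: blood pressure and pulse are taken after 5 minutes supine and then "repeated after the subject has been standing up for approximately 1 to 3 minutes".

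Section 6.2.3 then gives the definition. A subject qualifies with a systolic fall of 30 mmHg or more, a diastolic fall of 20 mmHg or more, or both, after 3 or more "minutes standing compared with the previous supine blood pressure, OR development of symptoms are considered to have orthostatic hypotension".

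Exclusion criterion 19 (Section 4.3.2) uses the same thresholds and takes the fall "after at least 3 minutes standing compared with the previous supine blood pressure", again with symptoms as an alternative. It lets the site repeat the measurement once before excluding a subject.

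Section 8.6.3 uses the classification in the safety results: "The number and proportion of subjects with orthostatic hypotension will also be summarized".

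**The concern.** The instruction on how to measure and the rule on what counts do not match. A site can do exactly what footnote e asks and obtain a reading that the definition does not cover.

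Two uses depend on it. One is eligibility: exclusion 19 needs a fall at 3 minutes or more, and the scheduled procedure does not guarantee a reading there. The other is a reported safety outcome for an event that Section 2.4 lists as a risk of the drug class, together with syncope. With approximately 70 centers planned, sites can reasonably settle on different reading times within the permitted window.

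**Working it through.** The protocol states no figure to reproduce, so the check sets the passages side by side.

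| Place | Purpose | Standing time |
|---|---|---|
| Table 1, footnote e | how to measure | about 1 to 3 min |
| Section 6.2.3, procedure | how to measure | about 1 to 3 min |
| Section 6.2.3, definition | who is a case | 3 min or more, or symptoms |
| Exclusion 19 | who is excluded | 3 min or more, or symptoms |
| Section 8.6.3 | what is reported | relies on the definition |

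1. **Overlap.** The measurement window is [1, 3] minutes and the definition window is [3, ∞) minutes. They intersect only at 3 minutes. The word for approximately blurs that point slightly but does not bring a 1- or 2-minute reading inside the definition.

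2. **A compliant case that cannot count.** Take a subject without symptoms whose systolic pressure is 30 mmHg lower at 1 minute. The size of the fall meets the threshold and the timing meets footnote e, but the timing fails Section 6.2.3 and exclusion 19. If no later reading is taken, it is unknown whether the fall was still present at 3 minutes.

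3. **A case that still counts.** The symptom limb carries no time condition, so a subject who develops symptoms on standing is classified whenever the cuff is read.

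4. **Size.** Let S be the proportion with symptoms, A the proportion with an asymptomatic qualifying fall at 3 minutes, and f the share of that second group whose reading was taken at 3 minutes. Applying the definition literally, the counted proportion is S + f × A. The protocol gives none of these values. Over the full range of f, the count runs from S (f = 0) to S + A (f = 1), so the possible loss runs from none to all of the asymptomatic cases.

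5. **The other direction.** If a site or the analysis counts falls seen at 1 or 2 minutes anyway, it may include falls that had gone by 3 minutes and lie outside the definition. The reported proportion then mixes two definitions.

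**The case against.** The strongest reply on the mismatch has four parts.

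- **A site can satisfy both texts by reading at 3 minutes.** True, but nothing tells it to, and reading at 1 minute is equally compliant.
- **Exclusion 19 states the 3-minute timing itself and permits one repeat.** This softens the eligibility effect, because a careful site has the rule in front of it. It does not help if the scheduled reading is taken early, shows no fall and is not repeated.
- **The summary is descriptive, and the analysis plan could set a counting rule.** A rule could say how early readings are treated, but it cannot supply a 3-minute reading that was never taken.
- **The same procedure applies in all blinded arms.** This stands: the documents give no reason to think that the timing favors one arm. The effect is on the level and consistency of the count.

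A reader might also infer something stronger: that the 18.0 mg arm goes unwatched at full dose until Day 7 and that an extra check around Day 3 or 4 is needed. Some facts point that way. Section 4.1.2 says "Subjects will receive treatment with study medication daily starting on Day 1 and up to Day 42 for a total of 6 weeks", Section 5.8 says "Dose modifications are not permitted", and Section 2.1 reports "Plasma asenapine concentration reached the steady state at around 72 hours after the first patch". The first scheduled post-dose check is then about 6 × 24 = 144 hours after a Day 1 patch, or 144 − 72 = 72 hours after steady state.

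The documents do not make this an error. Weekly scheduled assessment is a design choice that nothing in the text contradicts. Subjects are inpatients whose patches staff change daily, adverse events are recorded continuously, extra ECGs are allowed, and Section 4.3.3 lets the investigator withdraw a subject for safety. Table 3 puts 18.0 mg close to sublingual asenapine 10 mg twice daily in mean AUC (96.2/86.8 = 1.11) and lower in mean Cmax (4.68/6.56 = 0.71). Section 5.6 reports no clinically significant vital-sign or ECG findings in the earlier patient study. Postural readings are not required on Days 1 to 6, but adding them is a preference on which reasonable people differ.

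**Conclusion.** Wrong as written, in a narrow way. The reading instruction and the definition share only the 3-minute point, so an asymptomatic fall read at 1 or 2 minutes, as the schedule allows, cannot be classified as orthostatic hypotension. The Section 8.6.3 proportion can be too low or inconsistent between sites, and exclusion 19 can work differently across sites.

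The contradiction follows from the text alone and needs no assumption. Its numerical effect cannot be stated, because it depends on actual reading times and on how common asymptomatic falls are, and the protocol gives neither. The consequence is confined to a descriptive safety summary and one exclusion criterion. It does not touch the efficacy analysis, and it does not show that either dose is unsafe or that early monitoring is inadequate.

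**What to change.** In Table 1, footnote e and in Section 6.2.3, require the standing blood pressure and pulse at 3 minutes, in place of the present range. Asking only for 3 minutes or later would be weaker, because it sets no upper limit and would stop early falls from being seen. An additional reading at 1 minute may be kept for that purpose and reported separately.

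State that orthostatic hypotension, for both exclusion 19 and Section 8.6.3, is classified from the 3-minute reading or from symptoms. The thresholds and the text of exclusion 19 need no change.

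Cost: a site that now reads at 1 minute adds up to 3 − 1 = 2 minutes per visit. Table 1 marks vital signs at eight visits, so this is at most 8 × 2 = 16 minutes per subject over the study. No visit is added, and dose, endpoints, alpha and sample size stay as they are.

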4.2 Discussion of Study Design

This is a Phase 3, multi-center, placebo-controlled, randomized, double-blind, in-patient study designed to demonstrate the efficacy and safety of HP-3070 transdermal patches when used in subjects diagnosed with schizophrenia.

A parallel-group design was selected because it is free of the assumptions underlying competing designs (for example, crossover). A parallel group approach is considered the optimal study design to evaluate efficacy.

The use of a randomized double-blind design will minimize bias by randomly assigning the subjects to treatment arms, and ensuring that the subjects, the Investigators and site personnel, and the Sponsor/designee are blinded to the treatment allocations.

A placebo control will be used to allow for an unbiased assessment of treatment effects and safety data. The comparison with placebo is justified as this is an in-patient study and subjects will be closely monitored and study treatment will be discontinued and the subject will be returned to standard of care (SOC) treatment if their mental status deteriorates.

The study population will include male and female subjects, ≥ 18 years of age with a Diagnostic and Statistical Manual of Mental Disorders, Fifth Edition (DSM-5) diagnosis of schizophrenia who are in an acute exacerbation. These subjects represent an appropriate population in which to evaluate the efficacy of the HP-3070 patch.

The rationale for dose selection is described in [Section 5.6](#).

The 6-week duration is considered to be sufficient for achieving a steady state condition of HP-3070. This time period is also sufficient to evaluate changes in the primary and secondary outcome measures.

Subjects will be hospitalized throughout the study to ensure proper medical care, and to allow for the close monitoring of mental status and any potential negative effects of treatment.

Severity of illness and psychopathology will be measured using the PANSS and CDSS. The CGI-S and the CGI-I will be used to confirm clinical relevance of changes in the efficacy assessment scales. The efficacy measurements chosen for this study are standard validated instruments and these are commonly used to evaluate efficacy endpoints in subjects with schizophrenia who are in an acute exacerbation.

The primary efficacy endpoint is change from baseline to Week 6 in Positive and Negative Syndrome Scale (PANSS) total score. The PANSS scale is a standard validated instrument that is a gold standard in acute schizophrenia studies and is an appropriate instrument to evaluate efficacy in patients diagnosed with schizophrenia who are in acute exacerbation. This instrument is the primary efficacy endpoint that has been used for pivotal trials for several products such as SAPHRIS[®], Latuda[®], and Vraylar[®].

The key secondary endpoint is change from baseline to week 6 in the CGI-S score.

Noven Pharmaceuticals, Inc.
HP-3070-GL-04
HP-3070

35

The Clinical Global Impression – Severity (CGI-S) scale is an accepted, standard efficacy rating scale in acute schizophrenia trials. CGI-S is an acceptable key secondary variable: (i) based on precedence (SAPHRIS® and other approved antipsychotics); (ii) CGI-S assesses a domain of the illness other than that assessed by the primary efficacy variable, therefore, there is no redundancy with the primary efficacy variable (PANSS total score).

While the PANSS is the cornerstone for evaluation of efficacy of antipsychotic drugs in patients with schizophrenia who are in an acute exacerbation and is a useful clinical research tool, clinical implications of PANSS scores are not very well defined and the PANSS scores are not intuitively understood by clinicians; whereas, scores from the Clinical Global Impression (CGI) scale are better understood by clinicians and are better translated into clinical practice as they inform the clinician of the subject's overall clinical status.

The CGI-S is a valid and reliable clinician administered scale and has widespread use in psychiatry clinical trials. The CGI-S scale measures the clinician's global impression of the severity of illness at each time point taking into account the reported and observed symptoms in the past 7 days. In the HP-3070-GL-04 study, the CGI-S will be analyzed as change from baseline to Week 6. Inclusion of the CGI-S as key secondary endpoint in the HP-3070-GL-04 will facilitate replication of SAPHRIS® data.

The safety measures used in this study are standard safety measures which include AEs, concomitant therapy, clinical laboratory results, medical history, physical examination, vital signs, weight gain and ECGs. In addition, the AIMS, BARS, and SAS will be used to assess EPS. The C-SSRS will be used to assess suicidality. The C-SSRS facilitates prospective, systematic monitoring for emergence of suicidality within clinical trials and it is a low-burden, clinician-administered tool that covers the wide spectrum of suicidality from ideation to behavior. Skin irritation and discomfort reported by the subjects will be recorded as AEs. Skin irritation and discomfort at the patch application site is an important assessment because the condition of the skin may influence the absorption of the drug from the transdermal patch.

This study also includes assessment of patch adhesion and evaluation of amount of adhesive residue at the patch application site. Adhesion of transdermal patch to the skin is a critical factor and one of the most important functional properties directly related to drug delivery and therapeutic effect. Patch adhesion must be satisfactory in order for requirement for any clinical conclusions to be valid.

